## 7 DISCONTINUATION OF STUDY TREATMENT AND PARTICIPANT DISCONTINUATION/WITHDRAWAL

### 7.1 Discontinuation of Study Treatment

An individual patient will not receive any further IP (RXC004 or nivolumab) if any of the following occur;

- Patient decision to withdraw from further treatment with IP. The patient is, at any time,

free to discontinue treatment, without prejudice to further treatment

- Clinical or RECIST 1.1-defined radiological progression (symptomatically/clinically stable patients may continue treatment until symptomatic/clinical progression or second RECIST 1.1 progression [relative to the first 'on study treatment' RECIST 1.1 progression]). See Section 7.1.1 for details for continuing study treatment after RECIST1.1 defined progression
- An AE that meets discontinuation criteria in Appendix G or Table 14
- Pregnancy or intent to become pregnant
- Initiation of alternative anticancer therapy including another investigational agent
- Non-compliance with the study protocol that, in the opinion of the Investigator or Sponsor, warrants withdrawal from treatment with IP

Discontinuation from study treatment is NOT the same thing as a withdrawal from the study. If study treatment is permanently discontinued, the participant will remain in the study to be evaluated for safety, progression (if the patient discontinues for a reason other than progression) and survival. See the SoA for data to be collected at the time of discontinuation of study treatment and during follow-up.

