## **6.6 Dose Modification**

RXC004 dose reduction and interruption are permitted. Nivolumab dose reduction is not permitted but dose interruption/delay is permitted as per Appendix G.

RXC004 may be dose interrupted (withheld) until a clinically significant (any grade) and/or a grade  $\geq 3$  related adverse event resolves to baseline or  $\leq$  grade 2. RXC004 may also be withheld if it is necessary to give a concomitant medication that is a moderate or strong CYP3A4 inhibitor. RXC004 related colitis events should be managed as per Appendix J.

Adverse events that are assessed as being causally related nivolumab should be managed as per the Nivolumab Toxicity Management and Dose Modification Guidelines (Appendix G). If either agent is interrupted or discontinued for a related-AE the other agent (nivolumab or RXC004) may be continued if the patient is judged (by the investigator) to be receiving clinical benefit.

RXC004 and nivolumab dose interruption and stopping criteria are detailed in Table 14.

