**Table 14 Dose Modification and Stopping Criteria**

Event	Action
Colitis events (e.g. Colitis, ileitis, enterocolitis etc)	
Grade 1	If receiving RXC004, either as monotherapy or in combination with nivolumab; Reduce RXC004 to a lower dose (see Table 15 for dose reduction scheme) and manage as per Appendix J (and Appendix G if applicable)
Grade 2	If receiving RXC004, either as monotherapy or in combination with nivolumab Interrupt RXC004. Manage as per Appendix J and Appendix G if applicable. When event has resolved to Grade 1 a and steroids tapered to $\leq 10$ mg of prednisone per day (or equivalent), resume RXC004 at a lower dose (see Table 15 for dose reduction scheme) and nivolumab (if applicable) at 480 mg q4w. If event re-occurs after re-starting study treatment, then RXC004 and nivolumab (if applicable) should be permanently discontinued.
Grade 3	If receiving RXC004 monotherapy; Interrupt RXC004. Manage as per Appendix J. When event has resolved to Grade 1 a and steroids tapered to $\leq 10$ mg of prednisone per day (or equivalent), resume RXC004 at a lower dose (see Table 15 for dose reduction scheme). If event re-occurs after re-starting study treatment, then RXC004 should be permanently discontinued.
Grade 4	If receiving RXC004 in combination with nivolumab; permanently discontinue both agents and manage as per Appendix J and Appendix G.  If receiving RXC004, either as monotherapy or in combination with nivolumab; Permanently discontinue study treatment (both agents if applicable) . Manage as per Appendix J and Appendix G

Event	Action
Dysgeusia events	
Grade 1/2	RXC004 related; Consider dose reduction, depending on clinical symptoms Manage as per Appendix I Interrupt RXC004 treatment if dysgeusia is associated with >5kg weight loss from baseline
Grade 2 associated with a 10-20% decrease in body weight	RXC004 related; Manage as per Appendix I Reduce RXC004 to a lower dose (see Table 15 for dose reduction scheme).
Grade 2 associated with a >20% decrease in body weight	RXC004 related; Permanently discontinue RXC004. Nivolumab can continue if clinical benefit is judged by investigator.
Other adverse events	
Any event that meets discontinuation criteria for nivolumab (see Appendix G)	Permanently discontinue nivolumab. RXC004 can continue if clinical benefit is judged by investigator.

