Any event that meets nivolumab treatment hold (see Appendix G)	Interrupt nivolumab and manage as per Appendix G. Nivolumab can be re-started when event is resolved to ≤Grade 1 and any steroid taper completed (to ≤10 mg prednisone equivalent). RXC004 can continue whilst nivolumab is held if the patient is judged (by the investigator) to be receiving clinical benefit.
Grade 3 toxicity (1 st event)	RXC004 related; Interrupt RXC004 and provide supportive care, resume at a lower dose level when resolved (grade ≤ 2 or returns to baseline). See Table 15 for dose reduction scheme.
	Nivolumab related; See guidelines in Appendix G.
Grade 3 toxicity (subsequent recurrence of a previously experienced event)	RXC004 and/or nivolumab related; Permanently discontinue the related study treatment.

Event	Action
Grade 4 toxicity	RXC004 and/or nivolumab related; Permanently discontinue RXC004 and nivolumab (if applicable)
All Grade events	Study treatment can be interrupted or discontinued for any clinically significant AEs that in the investigator's opinion warrants treatment interrupted or discontinuation.
Bone events	
Confirmed (by imaging) RXC004 related fragility bone fracture (excluding grade 1 vertebral deformities)	Permanently discontinue RXC004. Nivolumab can continue if the patient is receiving clinical benefit as judged by the investigator.
Patients with a DXA scan showing $\geq 7\%$ worsening in BMD at lumbar spine or total hip compared to baseline	Permanently discontinue RXC004. Nivolumab can continue if the patient is receiving clinical benefit as judged by the investigator.
An individual increase in $\beta$ -CTX of CCI pg/ml from the baseline (screening) value or an individual measurement of CCI pg/ml	Permanently discontinue study treatment unless the patient has received clinical benefit (investigator assessment) and continued treatment is warranted.
COVID-19 infection	
Positive COVID-19 test	Interrupt RXC004, until acute symptoms have resolved.
Major surgery	
	Interrupt RXC004, resume at full dose. Nivolumab does not need to be interrupted.
	No stoppage is required for biopsy procedures.
Vomiting	
	If vomiting occurs shortly after RXC004 is swallowed, the dose may be replaced if all of the intact capsules can be counted. Resume with the following scheduled dose.
Missed RXC004 dose	

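### Protocol 7.1, read literally, ends both drugs for any adverse event meeting an Appendix G or Table 14 stopping criterion, while Section 6.6 and five rows of Table 14 stop only one

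*Protocol*

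**What the plan says.** Protocol 7.1 opens its list of stopping reasons with "An individual patient will not receive any further IP (RXC004 or nivolumab) if any of the following occur". The adverse-event entry in that list reads "An AE that meets discontinuation criteria in Appendix G or Table 14". The same lead-in covers pregnancy, patient decision and the start of another anticancer therapy.

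Protocol 6.6 gives a rule by agent: "If either agent is interrupted or discontinued for a related-AE the other agent (nivolumab or RXC004) may be continued", on condition that the investigator judges the patient to be benefiting. Table 14 applies that rule row by row:

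- Event meeting an Appendix G nivolumab stopping criterion: "Permanently discontinue nivolumab. RXC004 can continue if clinical benefit is judged by investigator".
- Grade 2 dysgeusia with more than 20% weight loss, related to RXC004: "Permanently discontinue RXC004. Nivolumab can continue if clinical benefit is judged by investigator".
- RXC004-related fragility fracture, and bone mineral density loss of 7% or more (two rows, same action): "Permanently discontinue RXC004. Nivolumab can continue if the patient is receiving clinical benefit as judged by the investigator".
- Recurrence of an earlier Grade 3 toxicity: "RXC004 and/or nivolumab related; Permanently discontinue the related study treatment".

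Other rows stop both agents. For Grade 4 toxicity the action begins "RXC004 and/or nivolumab related; Permanently discontinue RXC004 and nivolumab (if applicable". Table 14 and Appendix J also stop both for several colitis situations.

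**The concern.** Section 7.1 is where a site looks to decide whether a patient is off treatment. It sends the reader directly to Appendix G, which is guidance on nivolumab alone. A site that goes from 7.1 to Appendix G, finds a permanent stop and returns to the 7.1 lead-in never meets the Table 14 sentence that lets RXC004 continue. Section 8 allows no waivers, so the site needs one answer.

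Two sites could therefore handle the same event differently, and one of them would take away a drug that the more specific rule permits. A secondary consequence is for reporting. Discontinuations are part of the secondary safety endpoint, and SAP 4.12.1 tabulates permanent discontinuation of RXC004 and of nivolumab separately. Mixed practice across sites would blur those counts.

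**Working it through.** No arithmetic applies. The check sets the texts side by side for a patient on the combination.

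| Event | Section 7.1, literal | Section 6.6 and Table 14 |
|---|---|---|
| Appendix G nivolumab stopping criterion met, below Grade 4 (e.g. Grade 3 infusion reaction) | Both end | Nivolumab ends; RXC004 may continue |
| Grade 2 dysgeusia, weight loss over 20% | Both end | RXC004 ends; nivolumab may continue |
| RXC004-related fragility fracture | Both end | RXC004 ends; nivolumab may continue |
| Bone density loss of 7% or more | Both end | RXC004 ends; nivolumab may continue |
| Recurrent Grade 3 toxicity related to one agent | Both end | Only the related agent ends |
| Grade 4 toxicity | Both end | Both end |
| Grade 3 colitis on the combination; Grade 4 colitis; colitis of Grade 2 or higher recurring after restart | Both end | Both end |

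The first five lines conflict and the last two agree. Three further cases raise no conflict. Appendix J stops both agents when colitis steroids cannot be tapered within 12 weeks, and when colitis needs additional anti-inflammatory drugs. The β-CTX row of Table 14 refers to study treatment as a whole and makes its own exception for benefit.

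Can the parenthesis in the 7.1 lead-in be read as *whichever agent is concerned*? The lead-in governs every item in the list. Pregnancy and a new anticancer therapy plainly end both drugs, so for those items the parenthesis must mean both. Nothing marks a different meaning for the adverse-event item.

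Is the situation realistic? In the Phase 1 combination module, one of the 8 patients given RXC004 1.5 mg with nivolumab had a Grade 3 AST increase and drug-induced liver injury, attributed to both agents (Protocol 4.4.1.2). Appendix G makes Grade 3 hepatitis (AST or ALT 5 to 20 times the upper limit) a permanent nivolumab stop. For a first RXC004-related Grade 3 event, Table 14 interrupts RXC004 and resumes it at a lower dose, which Table 15 gives as 1.0 mg on the combination. Literal 7.1 ends RXC004. One patient is not a rate, and whether such a patient should resume is a clinical matter. The example shows only that the protocol gives two answers to a plausible event.

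**The case against.** The best defence is that 7.1 sets no adverse-event rule of its own. It points to Table 14 and Appendix G, which name the agent to stop, and a specific rule ordinarily governs a general one. The text below Table 15 and the separate SAP tabulations also show that decisions were meant to be made by agent. Continuation of the second drug is permissive, investigators may stop treatment for any clinically significant event, and literal 7.1 errs on the cautious side. Most of this stands. It establishes the likely intent and keeps the point small. It does not change what 7.1 says.

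Three stronger readings are tempting, and the documents do not support them.

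- *Counting rows.* A reader might size the conflict from Appendix G Table 19, where 19 rows end in a permanent nivolumab stop and 12 of those are not confined to Grade 4. But four of the 12 expressly include Grade 4 (pneumonitis, adrenal insufficiency, infusion reaction, and rash with SJS/TEN), where Table 14 stops both drugs. Three more carry no grade (immune-mediated encephalitis, Guillain-Barré syndrome, myasthenia gravis). A share of table rows is not a share of patients.
- *An effect on the efficacy analysis.* A reader might connect an early stop of RXC004 with the 4 weeks of intake in SAP 4.15. Continuation depends on investigator-judged benefit, and the documents give no basis for any shift in ORR, DCR or the evaluable set.
- *Further conflicts in Table 15 note b and Section 6.7.* Both refer to discontinuation criteria without naming an agent. Note b, however, sits in a table confined to RXC004-related events, and 6.7 does not cite 7.1. They would benefit from tidying but are not separate contradictions.

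**Conclusion.** The adverse-event entry in 7.1 is wrong as written: it conflicts with Section 6.6 and five single-agent rows of Table 14. This is a drafting inconsistency of minor importance. It concerns only patients receiving both drugs: Arm B, planned for 20 evaluable patients, and the Arm A combination phase, open to up to 20 who progress on monotherapy. How many would have a qualifying event cannot be estimated from the documents; few are expected.

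The conclusion rests on reading the 7.1 lead-in literally, as its other entries require. That Section 6.6 and Table 14 carry the intended rule is an inference from their greater detail and from the agent-level reporting in the SAP. No effect on sample size, error rates or the efficacy endpoints is claimed.

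**What to change.** Replace the adverse-event bullet in 7.1 with wording such as: *An adverse event meeting a discontinuation criterion in Table 14, Appendix G or Appendix J. This ends only the agent(s) specified there, and the other agent may continue as set out in Section 6.6. Where Table 14 (Grade 4 toxicity, colitis) or Appendix J requires both agents to stop, that rule takes precedence.*

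Both additions are needed. Without Appendix J, a colitis patient whose steroids cannot be tapered within 12 weeks could meet the prolonged-steroid row of Appendix G, lose nivolumab only and keep RXC004 through Table 14, although Appendix J stops both. The precedence sentence is needed because the Table 14 row for Appendix G events covers any event and does not say that the Grade 4 row overrides it.

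Optionally, make Table 15 note b refer to criteria for discontinuing RXC004, and give Section 6.7 matching agent-specific wording.

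The cost is a few sentences of protocol text, which could travel with the next amendment under the approval arrangements in Appendix A 1. Data collection, visit timing and the SAP do not change.

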RECIST 1.1 assessments (by CT/MRI) n		X		On study tumour assessments should occur q8w +/- 1 week (relative to first dose of IP) for the first 56 weeks, followed by q12w +/- 1 week until RECIST1.1 radiological progression x				On study tumour assessments should continue q8w +/- 1 week (relative to first dose of IP) for the first 56 weeks, followed by q12w +/- 1 week until RECIST1.1 radiological progression q, x				If a patient discontinues for a reason other than progression then tumour assessments should continue q8w +/- 1 week (relative to first dose of IP) for the first 56 weeks, followed by q12w +/- 1 week until RECIST1.1 radiological progression					
CCI h (mandatory unless unavailable at site) i		X*		On study CCI h assessments should occur at week 8 and week 16 +/- 1 week relative to first dose of IP.			On study CCI h assessments should occur at week 8 and week 16 +/- 1 week relative to first dose of combination										
Vitamin D3 and Calcium supplements			Patients should commence 800 IU vitamin D3 (Cholecalciferol) daily and 1000-1500 mg calcium daily supplements from ICF signature until RXC004 discontinuation														
Denosumab dosing y			120 mg sc Denosumab once every month from C0D1 until RXC004 discontinuation														
RXC004 dosing m			X (2 mg single dose)	Continuous daily dosing (2 mg QD)			Continuous daily dosing (1.5 mg QD)										
RXC004 diary			X	Review at each visit													

Table 1 – Arm A Schedule of assessments

Treatment Phase	Pre-treatment		RXC004 monotherapy			RXC004 + nivolumab combination j		Post-treatment				
	Pre-Screening	Screening	Cycle 0 (3-7 days)	Cycle 1 (28 day cycle)		Cycle 2 onwards (28 day cycles)	Pre-first Cycle	Cycle 1 onwards (28 day cycles)	IP Discontinuation	30 day Follow-up v	90 day Follow-up v	Survival follow-up
Window	n/a	-28 to -1	D1	D1	D15 +/- 1d	D1 +/- 3d		D1 +/- 3d	Within 7 days	+/- 3d	+/- 3d	q8w +/- 1wk
Nivolumab dosing								480 mg q4w +/- 3 days o				
RXC004 PK f			X		X	X		X	X			
Concomitant medication		X	X	X	X	X	X	X	X	X	X	
Adverse events		X	X	X	X	X	X	X	X	X	X	
Taste assessment z		X	At each visit – only if patient reports dysgeusia									
Survival status and post-discontinuation anti-cancer therapy p										X	X	X

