DXA scan		X	On Cycle 4 and Cycle 7 of RXC004 treatment and then every 7 RXC004 cycles thereafter whilst on study treatment							
Blood samples for bone turnover biomarkers ( $\beta$ -CTX)		X			X	X				
CCI [REDACTED] CCI [REDACTED]		X		X		X				
CCI [REDACTED] CCI [REDACTED] CCI [REDACTED]			X x		X	X				
CCI [REDACTED] CCI [REDACTED]			X x		X	X				

	Table 2 – Arm B (RXC004 + nivolumab combination) Schedule of assessments									
	Pre-Screening	Screening	Cycle 0 (3-7 days)	Cycle 1 (28 day cycle)		Cycle 2 onwards (28 day cycles)	IP Discontinuation	30 day Follow-up r	90 day Follow-up r	Survival follow-up
Window	n/a	-28 to -1	D1	D1	D15 +/- 1d	D1 +/- 3d	Within 7 days of discontinuation	+/- 3d	+/- 3d	q8w +/- 1wk
CCI [REDACTED] CCI [REDACTED]			X x		X	Cycle 2 only				
CCI [REDACTED] CCI [REDACTED]			X x		X	X	X			
CCI [REDACTED] CCI [REDACTED]			X x		X	X	X			
RECIST 1.1 assessments (by CT/MRI) j		X		On study tumour assessments should occur q8w +/- 1 week (relative to first dose of IP) for the first 56 weeks, followed by q12w +/- 1 week until RECIST1.1 radiological progression n						
CCI [REDACTED] (mandatory unless unavailable at site) i		X y	On study CCI [REDACTED] assessments should occur at week 8 and week 16 +/- 1 week relative to first dose of IP.							
Vitamin D3 and Calcium supplements			Patients should commence 800 IU vitamin D3 (Cholecalciferol) daily and 1000-1500 mg calcium daily supplements from ICF signature until RXC004 discontinuation							
Denosumab dosing t			120 mg sc Denosumab once every month from C0D1 until RXC004 discontinuation							
RXC004 dosing			X (1.5 mg single dose)	Continuous daily dosing (1.5 mg QD)						
RXC004 diary			X	Review at each visit						
Nivolumab dosing				480 mg q4w +/- 3 days k						

	Table 2 – Arm B (RXC004 + nivolumab combination) Schedule of assessments									
	Pre-Screening	Screening	Cycle 0 (3-7 days)	Cycle 1 (28 day cycle)		Cycle 2 onwards (28 day cycles)	IP Discontinuation	30 day Follow-up r	90 day Follow-up r	Survival follow-up
Window	n/a	-28 to -1	D1	D1	D15 +/- 1d	D1 +/- 3d	Within 7 days of discontinuation	+/- 3d	+/- 3d	q8w +/- 1wk
RXC004 PK f			X		X	X	X			
Concomitant medication		X	X	X	X	X	X	X	X	
Adverse events		X	X	X	X	X	X	X	X	
Taste assessment u		X	At each visit – only if patient reports dysgeusia							

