#### 8.1.1 Tumour assessments

Tumour assessments utilize images from CT or MRI, collected during screening/baseline and at regular (follow-up) intervals during the study. The same imaging method should be used throughout the study. It is important to follow the tumour assessment schedule as per the SoA. Tumour assessments will continue until RECIST1.1-defined radiological progression. Patients treated with RXC004+nivolumab that continue treatment after RECIST1.1 progression, will continue tumour assessments until second RECIST1.1 defined radiological progression (relative to the initial RXC004+nivolumab progression event).

Sites will be required to store electronic copies of all scans, and the Sponsor may arrange for possible centralised storage of all imaging data. Centralised storage of imaging data would be possible to support an independent centralized review of disease assessments.

In addition, if available, the last 2 imaging scans taken prior to the screening scan for this study and/or their reports should be kept for possible central/sponsor review.

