3.2.1.5 Progression Free Survival (PFS)

PFS is defined as the time from first dose of study treatment (Day 1) until the date of disease progression or death (by any cause in the absence of progression), regardless whether the patient withdraws from the assigned study treatment or receives another anticancer prior to progression.

Patients who have not progressed or died at the time of analysis will be censored at the time of the latest date of RECIST 1.1 assessment of their last evaluable scan, however if the patient progresses or dies after 2 or more missed scheduled scanning visits (Progression/Death date - Last available scan date \geq 16 +1 weeks), the patient will be censored at the time of their last evaluable scan prior to the missing scan visits. If the patient has no evaluable visits or does not have baseline data, they will be censored at 0 days. However, if the patient dies within 2 scan visits of first dose (within 16 +1 weeks from first dose date without a post baseline scan) then its death date will be treated as their progression date. PFS was set as secondary efficacy endpoint both for arm A and arm B, and PFS time is defined as:

$$\text{PFS (days)} = \text{Date of documented PD, Death or last RECIST 1.1 assessment} - \text{first dose of study treatment (C0D1)} + 1$$

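### Protocol 7.1 and Table 1 conflict with 4.1 and 8.1.1 on scanning after clinical progression; where a site follows 7.1/Table 1, the descriptive PFS rates are biased upward

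*Protocol*

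**What the plan says.** Two sets of passages govern scanning after treatment stops.

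- **Protocol 7.1 (both arms)** gives as a single reason for stopping treatment "Clinical or RECIST 1.1-defined radiological progression". It then says that a discontinued patient remains in the study to be evaluated for safety, "progression (if the patient discontinues for a reason other than progression) and survival". For the data to be collected it refers to the schedule of assessments.
- **Protocol Table 1 (Arm A), RECIST row, post-treatment:** "If a patient discontinues for a reason other than progression then tumour assessments should continue q8w +/- 1 week", with RECIST 1.1 radiological progression as the end point of that scanning.
- **Protocol Table 2 (Arm B), RECIST row:** "On study tumour assessments should occur q8w +/- 1 week (relative to first dose of IP) for the first 56 weeks", then every 12 weeks to RECIST progression. It has no instruction specific to patients off treatment.
- **Protocol 8.1.1:** "Tumour assessments will continue until RECIST1.1-defined radiological progression". Protocol 4.1 and SAP 6.1 say the same, with no exception for clinical progression.

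SAP 3.2.1.5 counts progression or death regardless of withdrawal from study treatment. Patients with neither "will be censored at the time of the latest date of RECIST 1.1 assessment of their last evaluable scan". A patient who "progresses or dies after 2 or more missed scheduled scanning visits", defined as a gap of at least 16 + 1 weeks, is censored back to the last evaluable scan. SAP 6.1.4 adds that PD may also be a worsening of the patient's condition, including symptoms. SAP 3.2.1.5 does not say whether that counts as a PFS event.

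**The concern.** In 7.1 the word progression covers both clinical and RECIST progression when it defines why treatment stops. A few lines later the same unqualified word decides who is still followed for progression. A site applying 7.1, or the Table 1 cell, to a patient stopped for clinical progression without a RECIST PD scan could reasonably stop scanning.

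A PFS definition that ignores treatment withdrawal needs scans after withdrawal. Without them, a visibly progressing patient leaves the risk set as progression-free, so the censoring depends on prognosis. PFS is a secondary endpoint in both arms, presented without a formal comparison between them. Protocol 4.3.1 says that PFS and the other secondary endpoints will be weighed because DCR is hard to interpret in a single arm. An upward bias in PFS would therefore flatter the evidence used to judge activity.

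**Working it through.** The plan gives no figure to reproduce. PFS has no event target, and no rate of clinical-first progression is stated. The check follows the censoring rule and then sizes its effect by simulation.

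**One invented patient.** Stable disease at the week 8 scan (day 56), stopped for clinical progression on day 80, no further scan.
- Death on day 150: 150 − 56 = 94 days, under 17 × 7 = 119, so PFS event on day 150.
- Death on day 200: 200 − 56 = 144 days, at least 119, so censored at day 56.
- Had scanning continued and shown PD at week 16, the event would fall on day 112 in both cases.

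Both outcomes lengthen PFS: the first dates the event late, the second removes it.

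**Inputs from the documents.** Scans every 56 days (Tables 1 and 2); the 119-day rule (SAP 3.2.1.5); cut-off about 24 weeks after the last patient's Cycle 1 Day 1 (Protocol 9.4.1); reference median PFS about 2 months and OS about 6 months (Protocol 2.3.3).

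**Assumptions.** Exponential times; a 2-month median to underlying progression; a 4-month median from progression to death (roughly 6 − 2); uniform 12-month accrual; 10%, 20% or 30% of progressions clinical only. Alternative medians are 3/4 and 4/6 months.

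**Rules compared**, with T the time of progression and L = 56 × floor(T/56) the last scan before it:
- Scans to RECIST PD: event at the earlier of L + 56 and death.
- 7.1/Table 1 followed: for a clinical-only progressor, event at death if death − L < 119 days, otherwise censored at L.

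**Share censored.** For progression midway between scans, 119 − 28 = 91 days remain, or 91/30.4375 = 2.99 months. With a 4-month median, P(death in that time) = 1 − 2^(−2.99/4) = 0.40. The simulation also gives about 40% as death events, so about 60% are censored. With a 6-month median, the hand value is 1 − 2^(−2.99/6) = 0.29 and the simulated value 28%.

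**Kaplan-Meier 6-month PFS**, 400,000 simulated patients per scenario:

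| Medians: to progression / then to death (months) | Clinical-only share | Scans to RECIST PD | 7.1/Table 1 followed | Difference (points) |
|---|---|---|---|---|
| 2 / 4 | 10% | 14.6% | 16.0% | +1.4 |
| 2 / 4 | 20% | 14.7% | 17.8% | +3.1 |
| 2 / 4 | 30% | 14.7% | 19.6% | +4.9 |
| 3 / 4 | 10% | 27.8% | 29.8% | +2.0 |
| 3 / 4 | 20% | 27.7% | 31.8% | +4.1 |
| 3 / 4 | 30% | 27.8% | 34.3% | +6.5 |
| 4 / 6 | 10% | 38.2% | 40.7% | +2.5 |
| 4 / 6 | 20% | 38.3% | 43.4% | +5.1 |
| 4 / 6 | 30% | 38.3% | 46.3% | +8.0 |

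In the 2/4 case, 3-month PFS is 52.9%, 54.9% and 56.9% against about 51%. Median PFS is 3.68 against about 3.35 months. In the other cases the median is unchanged, except 3.89 against 3.68 months at 3/4 with 30%. Events cluster on the 8-week scan grid, so the median is insensitive.

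**Primary endpoints.** A patient without a confirmed response, or stable disease on a scan at 15 weeks or later, is not a DCR success (SAP 3.2.1.3). Stopping scans early cannot create one. SAP 4.15 lets patients who progressed before the first radiographic assessment count in the evaluable set.

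**The case against.** The strongest reply is that this is loose wording and not a rule to stop scanning. The Table 1 cell sits in a RECIST row and its own sentence ends at RECIST progression, so its exception can be read as RECIST progression. Protocol 4.1 and 8.1.1, the on-study rows of both tables and SAP 6.1 all point that way. This stands to the extent that a reader might infer that the protocol directs scans to end at clinical progression, and the documents do not support that: they conflict. The conflict still matters, because 7.1 defines its own term broadly, sends sites to the schedule, and for Arm A the schedule repeats the exception.

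SAP 6.1.4 might let an investigator record clinical worsening as PD, in which case there is no censoring. But SAP 3.2.1.1 takes overall response only from RECIST visits, and 3.2.1.5 names no clinical event. The point is unresolved, which is itself a reason to settle it.

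The size is also open to challenge. The clinical-first share is assumed, and the comparator supposes that every such patient is scanned and shows PD at the next visit, so the recoverable bias is smaller. Patients treated beyond RECIST PD who later stop clinically already have an event. With 20 evaluable patients, the 3.1-point shift in the middle base case is about 0.6 of a patient (0.031 × 20), against a binomial standard error near 8 points (√(0.15 × 0.85/20) = 0.080). All of this stands and limits the weight of the point. It does not remove a bias that was upward or nil in every scenario.

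**Conclusion.** The concern holds as a conflict between passages with a predictable effect on PFS. If 7.1/Table 1 is followed, 6-month PFS is overstated by about 1 to 5 points in the base case, and by about 2 to 8 points with the longer medians. Both ranges assume exponential times and a 10% to 30% clinical-first share, which the documents neither give nor exclude. Median PFS is little affected.

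Three stronger readings are not supported. Not every clinical progressor is censored: about 40% in the base case become events through death inside 17 weeks. The primary DCR and ORR are not materially biased. Nor can it be concluded that no scan is due at the discontinuation visit, because the columns of the schedule table cannot be aligned reliably in the available text. No go/no-go decision is shown to turn on the bias. The correction is worthwhile because it is cheap and the bias runs in the drug's favour.

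**What to change.** 1. In Protocol 7.1 and the Table 1 post-treatment cell, replace 'other than progression' with 'other than RECIST 1.1-defined radiological progression'. Add the same sentence to Table 2. This concerns follow-up scans only, not when treatment stops.
2. In SAP 3.2.1.5, state that the primary PFS event is RECIST 1.1 PD or death, and bring SAP 6.1.4 into line.
3. Report one sensitivity PFS that counts discontinuation for clinical progression as an event on its date. In the base case this gives 14.3%, 14.2% and 13.9% at 6 months, within one point of the result with continued scans. It also covers patients whose scans have already stopped, which an amendment cannot recover.

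The cost is a few words in an amendment and one extra run. SAP 4.4.1 already summarises the primary reason for end of treatment; whether the case report form separates clinical from radiological progression should be confirmed. No scans are added beyond those 8.1.1 requires. Some declining patients will still miss scans, and PFS may look slightly less favourable.
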